The study will utilise a non-interventional longitudinal population-based retrospective cohort design. It will be conducted using secondary data derived from multiple databases which record longitudinal medical data. The data sources include registries in Finland, Denmark, France, Germany and the United States of America (USA). The unit of analysis is a pregnancy in women with moderate/severe SLE. Therefore, a woman may contribute more than one pregnancy to the study.

The two primary outcomes of interest are a composite of MCM diagnosed in the offspring at the end of the pregnancy or until one year of age, based on the ICD-10 diagnostic codes (or other country specific coding system), as recorded in the data sources; and select pregnancy loss outcomes (a composite of spontaneous abortion and stillbirth), diagnosed in the woman from last menstrual period + 2 weeks (LMP2) up to end of pregnancy.

The secondary outcomes of interest are a composite of mCM (diagnosed in the offspring at the end of the pregnancy or until one year of age), adverse pregnancy outcomes (diagnosed in the woman from LMP2 up to end of pregnancy), adverse birth outcomes (diagnosed in the offspring at birth), investigated separately.

For congenital malformation (CM), birth, and infant outcomes, the population of study will be limited to offspring for whom mother-offspring record linkage is available within each data source. However, for pregnancies that end in a spontaneous abortion, an elective termination of pregnancy, or stillbirth where there is a diagnosis of MCM in the mother's record, mother-offspring linkage will not be required.

The exposure of interest is *in utero* exposure to anifrolumab and/or *in utero* exposure to SLE SOC between LMP2 (derived from last menstrual period or, if missing, gestational age) and end of pregnancy or occurrence of the outcome of interest (whichever comes first). For the primary outcome of MCM, the exposure ascertainment period is restricted to the etiologically relevant period of the first trimester. Exposure information will be derived from outpatient visits and/or prescription data, as recorded in the data source for each country. Country-specific cohorts of eligible women or woman/offspring units will be identified for each outcome.

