Adverse infant growth	Infant growth	Live offspring	min 12 months prior to LMP2	from LMP2 to end of pregnancy	birth	from birth to max 1y of age	NA

¹ The exposure window is considered from conception (defined as LMP2) to the end of pregnancy (first trimester only for MCM) or censoring, whichever occurs first.

Abbreviations used in the table: NA, Not applicable; Min, Minimum; Max, Maximum; 1 y, 1 year of age; LMP2, Date of conception (last menstrual period + 2 weeks)

For the main analysis, a comparable group of pregnant women, with moderate/severe SLE, will be selected as the comparator group. The current indication for anifrolumab use is as an add-on therapy for moderate/severe SLE. Therefore, the most suitable comparator population is a population of women with moderate/severe SLE. Additionally women with moderate/severe SLE are at increased risk of adverse outcomes during pregnancy, (as a result of SLE disease severity, SLE disease activity and effects of medication use) compared to non-SLE pregnant women (27). However, as treatment with anifrolumab may reduce SLE severity, it is possible that not all anifrolumab exposed pregnancies would be of moderate/severe severity. Therefore, a sensitivity analysis which includes all anifrolumab users (regardless of disease severity) will be conducted. Details of this sensitivity analysis are provided in Section 9.7.5.

Aggregated country-specific results for the primary objectives will be combined via a meta-analytic approach, providing a pooled estimate across all data sources.

[figure not shown]

Figure 1: Overview of the study design, for MCM and mCM

- a. Diagnosis of SLE in the mother before pregnancy
- b. Women with a continuous enrolment in the database for ≥ 12 months prior to conception (defined as LMP2)

- c. Singleton pregnancy, mother-offspring linkage. Mother-offspring linkage will not be required for spontaneous abortion, stillbirth, and ectopic pregnancy where the diagnosis/reason provided is MCM
- d. Women with a history of CM or chromosomal abnormalities
- e. Pregnancy associated with in vitro fertilisation (IVF), pregnancy with unknown date of conception
- f. Comorbidities and covariates measured prior to index date may include maternal diabetes, maternal pre-pregnancy body mass index (BMI), obstetric history

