- i. First of the following: ectopic pregnancy, spontaneous abortion, elective termination of pregnancy, stillbirth, select pregnancy loss outcomes (composite of spontaneous abortion and stillbirth) composite of foetal loss (considering the presence at least one of the following: spontaneous abortion, ectopic pregnancy, elective termination of pregnancy and stillbirth), infections requiring hospitalisation during pregnancy, emergency caesarean section, death, emigration, end of study period (end of pregnancy)
- j. Covariates measured at index date may include maternal socioeconomic status (SES), age at LMP2
- k. For infections requiring hospitalisation during pregnancy, follow-up is from enrolment until the end of pregnancy

[figure not shown]

Figure 3: Overview of the study design, for adverse birth outcomes

- a. Diagnosis of SLE before pregnancy
- b. Women with a continuous enrolment in the database for ≥ 12 months prior to conception (defined as LMP2)
- c. Singleton pregnancy, mother-offspring linkage

- d. Women with a history of CM or chromosomal abnormalities (information related to history of CM and chromosomal abnormalities can also be retrieved from clinical records (birth and maternal clinical records) regarding the current pregnancy)
- e. Pregnancy associated with in vitro fertilisation (IVF), date of conception cannot be established
- f. Comorbidities and covariates measured prior to index date may include maternal diabetes, maternal pre-pregnancy BMI, obstetric history
- g. Exposure to SLE SOC will be assessed in the exposed and comparator groups at LMP2 with a look-back period of 5-half-lives of relevant drug. Exposure to anifrolumab will be assessed from LMP2 until end of pregnancy with a maximum look-back period of 16-weeks (time for anifrolumab concentration to fall below the LLOQ for 95% of patients) prior to LMP2
- h. Comorbidities and covariates measured during pregnancy may include maternal smoking, alcohol and substance abuse, gestational diabetes
- i. Covariates measured at index date may include maternal socioeconomic status (SES), age at LMP2
- j. First of the following: preterm birth, small for gestational age, death, emigration, end of study period (delivery/birth)

[figure not shown]

Figure 4: Overview of the study design, for adverse outcomes related to infant growth up to 1 year of age

- a. Diagnosis of SLE before pregnancy

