Additional exclusion criteria to be applied after data extraction to create an *unexposed source population* (mirroring the exposed source population, except for the exposure itself):

- Women treated with anifrolumab during pregnancy and/or during the 16-week period prior to LMP2
- Pregnancies whose date of conception cannot be established

STEP 3

Step to create *exposed to anifrolumab study population* and *unexposed to anifrolumab study population*.

STEP 3A and 3B – exposed and unexposed to anifrolumab study population

Additional inclusion criteria to be applied to the exposed and unexposed source population for creating a post-data extraction overarching *exposed and unexposed study population* with only moderate to severe SLE (mirroring the exposed study population, except for the exposure itself):

- Women with moderate to severe SLE (severity assessment is based on the SLE severity algorithm, see Figure 7)

Additional exclusion criteria to be applied to the exposed and unexposed source population for creating a post-data extraction overarching *exposed and unexposed study population* (mirroring the exposed study population, except for the exposure itself):

- Women with mild SLE (severity assessment is based on the SLE severity algorithm, see Figure 7)

⁷ For example, a patient can be considered continuously enrolled in a specific time period if that patient had a contact with healthcare services (such as drug prescription/administration or hospitalisation) prior to that period and if emigration or death were not notified after this contact. Criteria to define continuous enrolment in the database are country specific and will be detailed in the SAP.

⁸ Exposure to SLE SOC will be assessed from LMP2 until end of first trimester for the outcome of MCM, and from LMP2 until end of pregnancy for all other outcomes. A look-back period of 5-half-lives of relevant drugs will be considered.

- Women with a history of CM or chromosomal abnormalities and genetic syndromes (according to available records)⁹, before delivery
- Women prescribed a confirmed teratogenic drug prior to LMP2 until end of first trimester (for MCM outcome) or end of pregnancy (all other pregnancy outcomes), with a look back period of 5-half-lives of relevant drug, in both the exposed and unexposed groups (see [Table 20](#))

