To address the research questions related to the primary, secondary, and exploratory outcomes, cohorts and subgroups will be created. Additional selection criteria, to form the relevant population for each specific outcome, will be applied (*STEP 4*).

STEP 4 - Cohorts and sub-cohorts

For the purpose of the evaluation of MCM (primary outcome), the *MCM* cohort will be derived from the study populations ([Table 5](#)) and will include live and non-live offspring from mothers diagnosed with SLE (regardless of the exposure to anifrolumab, i.e., sub-cohorts *MCM_exp+MCM_unexp*).

For the purpose of the evaluation of mCM (secondary outcome), the *mCM* cohort will be derived from the study populations ([Table 5](#)) and will include live and non-live offspring from mothers diagnosed with SLE (regardless of the exposure to anifrolumab, i.e., sub-cohorts *mCM_exp+mCM_unexp*).

For the purpose of the evaluation of select pregnancy loss outcomes (composite of spontaneous abortion and stillbirth; primary outcome), and secondary outcomes (adverse pregnancy outcomes), the *pregnancy* cohort will be derived from the study populations ([Table 5](#)) and will include pregnant women diagnosed with SLE (regardless of the exposure to anifrolumab, i.e., sub-cohorts *pregnancy_exp+pregnancy_unexp*).

For the purpose of the evaluation of adverse birth outcomes (secondary outcomes), the *birth* cohort will be derived from the study populations ([Table 5](#)) and will include live offspring from mothers diagnosed with SLE (regardless of the exposure to anifrolumab, i.e., sub-cohorts *birth_exp+birth_unexp*).

For the purpose of the evaluation of adverse outcomes related to infant growth up to one year of age, the *infant* cohort will be derived from the study populations ([Table 5](#)) and will include live offspring from mothers diagnosed with SLE (regardless of the exposure to anifrolumab, i.e., sub-cohorts *infant_exp+infant_unexp*).

⁹ Several CMs in the mother are due to genetic syndromes/ microdeletions and chromosomal abnormalities which are heritable. These genetic syndromes/microdeletions are also causally associated with the outcomes of interest. The list of these syndromes/microdeletions and chromosomal abnormalities are provided in [Appendix D. Exemplar Codelists](#).

Additional inclusion and exclusion criteria to derive the abovementioned cohorts and sub-cohorts are listed in [Table 5](#).

Table 5: Cohorts and sub-cohorts as described in STEP 4, by objective

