MCM (defined as a composite of all major MCMs) among live and non-live offspring: The first primary outcome of interest is MCM occurring in live or non-live offspring. MCM is defined as defects of prenatal origin that have either cosmetic or functional significance to the child's health, development, or survival. MCM ascertainment will be based on the presence of an ICD-10 code (or other database specific coding system [codes to be adapted to the coding systems used in each of the data sources]) in the database. These ICD-10 codes will be classified according to the EUROCAT (Description of the Congenital Anomaly Subgroups in EUROCAT Guide 1.5) classification scheme, as four of the five data sources are in Europe (41). As there are some differences in the classification of MCMs by different classification schemes, the USA CDC definition of MCM as an abnormality of body structure or function that is present at birth, is of prenatal origin (i.e., birth defect), has significant medical, social, or cosmetic consequences for the affected individual, and typically requires medical intervention as implemented by the Metropolitan Atlanta Congenital Defects Program (MACDP) will also be implemented as a sensitivity analysis (see Section 9.7.5) (15, 24). The list of the MCM and their respective ICD-10 codes are presented in Table 22a using the EUROCAT classification. The MACDP 6-digit code defect list for major congenital malformations is presented in Table 22b.

The MCM ascertainment period is defined as:

- for live births, from birth until 1 year of age
- for non-live births (spontaneous abortion and stillbirth) an ICD-10 of MCM as the diagnosis at end of pregnancy
- for elective terminations, an ICD-10 code of an MCM as the reason for the termination at termination of pregnancy.

Select pregnancy loss outcomes (composite of spontaneous abortion and stillbirth) among all pregnancies

The second primary outcome of interest is select pregnancy loss outcomes, a composite of spontaneous abortion and stillbirth (Table 24).

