	CM	Adverse pregnancy outcomes						Adverse birth outcomes	
	MCM/mCM	Ectopic pregnancy	Spontaneous abortion	Elective termination of pregnancy	Stillbirth	Infections requiring hospitalisation during pregnancy	Emergency C-section	Preterm birth	SGA
Mother									
Age at conception (LMP2)	×	×	×	×	×	×	×	×	×
Socioeconomic status (before or at start of exposure)	×	×	×	×	×	×	×	×	×
Health care utilisation (before or at LMP2)	×	×	×	×	×	×	×	×	×
SLE-related comorbid conditions (before or at start of exposure)	×	×	×	×	×	×	×	×	×
SLE SOC (before or at start of exposure)	×	×	×	×	×	×	×	×	×
SLE activity algorithm (before or at start of exposure)	×	×	×	×	×	×	×	×	×
Autoimmune conditions (before or at start of exposure)	×		×	×	×		×	×	×
Co-medications (non-SLE SOC) (before or at start of exposure)	×	×	×	×	×	×	×	×	×
Smoking (before or at LMP2)	×	×	×	×	×	×	×	×	×
Alcohol abuse (before or at LMP2)	×	×	×	×	×	×	×	×	×
Substance abuse (before or at LMP2)	×	×	×	×	×	×	×	×	×
Gestational diabetes (before or at LMP2)								×	×
Pre-pregnancy obesity (before or at LMP2)	×		×		×		×	×	×
History of pre-eclampsia (before or at LMP2)	×				×				
Pre-pregnancy hypertension (before or at LMP2)	×				×	×	×	×	×

	CM	Adverse pregnancy outcomes						Adverse birth outcomes	
	MCM/mCM	Ectopic pregnancy	Spontaneous abortion	Elective termination of pregnancy	Stillbirth	Infections requiring hospitalisation during pregnancy	Emergency C-section	Preterm birth	SGA
Mother									
Pre-pregnancy diabetes (before or at LMP2)	×		×		×	×	×	×	×
Previous spontaneous abortions (before or at LMP2)	×		×	×	×			×	
Previous stillbirth (before or at LMP2)	×				×				
Previous preterm birth (before or at LMP2)								×	
Previous SGA (before or at LMP2)									×
Offspring									
Year of conception	×	×	×	×	×	×	×	×	×

- Omitted from this list are potential risk factors and/or potential mediators between SLE treatments and CM that are exclusion criteria in this study (as defined in Section 9.2.2):
 - *mother*: history of CM or chromosomal abnormalities and genetic syndromes before delivery and women prescribed a confirmed teratogenic drug (including but not limited to warfarin, angiotensin converting enzyme inhibitors, antineoplastic agents, isotretinoin, misoprostol, or thalidomide), at LMP2 with a look back period of 5-half-lives of relevant drug, to account for prescriptions/dispensations/administrations that may have led to exposure during pregnancy.
 - *offspring*: adopted children.

SLE Severity and Activity Identification

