- Misclassification may occur in the derivation of date of conception. When based on LMP, the derivation of date of conception assumes an average cycle length of 28 days and that conception occurred mid-cycle. The LMP is also subject to accuracy of recall by the woman, regularity of her cycles, and variations in the interval between bleeding and anovulation. When based on gestational age, the degree of misclassification depends on the method and accuracy of the gestational age assessment. However, the misclassification is expected to be within a range of days for most patients.

- Immortal time bias cannot be ruled out. Immortal time is the period during which the outcome of interest cannot occur because of the study design (108). In this study, there is an immortal time because a pregnancy must “survive” until initiation of treatment to be considered as exposed. Nevertheless, it is expected that most pregnant women would have exposure to anifrolumab in the first trimester, and exposure to anifrolumab initiation in the second or third trimester is not expected to be frequent. Adding to this, most outcomes that terminate a pregnancy, such as a spontaneous abortion or an ectopic pregnancy, are expected to happen in the first trimester, thus minimising the impact of this bias.
- The probability of receiving anifrolumab may be related to the length of pregnancy, to some extent. The patients with longer pregnancies have more opportunity (i.e., time) to be prescribed anifrolumab, while the patients with shorter pregnancies have less opportunity (i.e., time) to be prescribed anifrolumab. This may cause a bias in the analysis as shorter pregnancies are more likely to be included in the study cohort unexposed to anifrolumab.
- Both maternal and paternal disease history can be important predictors of the risk of adverse pregnancy outcomes because of shared environmental and genetic risk factors. For this study, no paternal data will be available because linkage to paternal data is not possible for most data sources. Therefore, offspring whose fathers have a history of CM before pregnancy will not be excluded, and no adjustments can be made for potential confounders related to fathers.

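### The maternal malformation-history exclusion stays open until delivery, so a foetal malformation coded during the pregnancy can exclude an MCM case from the first primary analysis

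*Protocol*

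**What the plan says.** The exclusion sits in STEP 3A and 3B of Section 9.2.2. It applies to exposed and unexposed women alike, before any outcome cohort is derived: "Women with a history of CM or chromosomal abnormalities and genetic syndromes (according to available records)⁹, before delivery". The note under Table 7 in Section 9.3.3 repeats the time limit: "history of CM or chromosomal abnormalities and genetic syndromes before delivery and women prescribed a confirmed teratogenic drug".

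Footnote 9 gives the reason: "Several CMs in the mother are due to genetic syndromes/ microdeletions and chromosomal abnormalities which are heritable". The footnote points to Appendix D for the list of conditions.

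The design figures in Section 9.1 carry the criterion as note d. For the MCM design (Figure 1) it reads only "Women with a history of CM or chromosomal abnormalities". Figure 3, for adverse birth outcomes, adds that the information "can also be retrieved from clinical records (birth and maternal clinical records) regarding the current pregnancy".

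On the outcome side, the Abstract waives mother–offspring linkage for pregnancies ending in spontaneous abortion, elective termination or stillbirth "where there is a diagnosis of MCM in the mother's record". Section 9.3.2 starts MCM follow-up at LMP2 and, for terminations, counts "an ICD-10 code of an MCM as the reason for the termination at termination of pregnancy".

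**The concern.** An eligibility criterion for a cohort followed from LMP2 should close at LMP2. This one remains open through the whole pregnancy, when foetal malformations are found on scans and may be coded in the mother's record. For non-live pregnancies that record is also where the outcome is found. If the person building the cohort cannot tell whose malformation a code describes, eligibility for the MCM analysis comes to depend on the MCM outcome.

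The clearest case is a termination for foetal anomaly, because the anomaly has to be diagnosed before the pregnancy ends. The protocol wants to keep exactly these cases, since it waives linkage for them.

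Two things are at stake. Equal loss in both groups understates the absolute MCM risk (Objective 1) and costs power. Unequal loss biases the RR (Objective 2), which is judged against a margin of 2.5.

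**Working it through.** **The windows side by side**

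- SLE diagnosis (Section 9.2.2, STEP 2): before pregnancy.
- Continuous enrolment (STEP 2): at least 12 months before LMP2.
- Paternal counterpart (Section 9.9): "offspring whose fathers have a history of CM before pregnancy will not be excluded", so dated before pregnancy.
- Maternal CM history (STEP 3 and the note under Table 7): up to delivery.
- MCM follow-up (Section 9.3.2): from LMP2.

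The maternal criterion is the outlier, and it overlaps MCM follow-up for the whole pregnancy.

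**Is there anything that separates the codes?** Footnote 9 promises a list in Appendix D. Table 18, which holds the exclusion codes, covers multifetal pregnancy and IVF and has no malformation entry. The malformation and chromosomal code lists in the appendix are the outcome lists, Tables 22a and 23. Table 22a counts genetic disorders, including Q87 and Q90–Q93, as MCM. No sentence says how to tell a maternal code from a foetal one in the mother's record.

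**Reproducing the stated power.** Inputs (Section 9.5): MCM prevalence 7%, margin RR 2.5, one-sided alpha 2.5%, true RR 1.0, 10% uptake, 2032 report. Exposed pregnancies in the three contributing sources: 102 + 114 + 116 = 332. Expected exposed events: 332 × 0.07 = 23.2 (Table 11 shows 7 + 7 + 8 = 22 after rounding).

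The simulation followed Section 9.5.1.3: binomial events per source, variance of log RR = 1/a + 1/b (a and b are the event counts in the two groups), fixed-effect inverse-variance pooling, and the share of 95% upper limits below 2.5. With 40,000 runs it gave 96.1% (1:2) and 98.3% (1:3), against the stated 96% and 98%.

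**Equal loss, true RR 1, ratio 1:2.** Let f be the share of MCM cases excluded. The protocol gives no value, so f is assumed. Excluded cases leave the denominator too:

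observed risk = 0.07(1 − f) / (1 − 0.07f)

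- f = 0.2: 0.056/0.986 = 5.7%; about 4.6 exposed cases lost; power about 90%.
- f = 0.3: 0.049/0.979 = 5.0%; about 7.0 exposed cases lost; power about 85%.

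**Unequal loss, true RR 2.5** (exposed risk 0.07 × 2.5 = 0.175), with the shares again assumed:

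- 30% of exposed and 20% of comparator cases: [0.1225/0.9475] / [0.056/0.986] = 0.1293/0.0568 = 2.28.
- 50% and 30%: [0.0875/0.9125] / [0.049/0.979] = 0.0959/0.0501 = 1.92.
- 40% and 20%: [0.105/0.93] / 0.0568 = 1.99. The simulated chance of wrongly ruling out 2.5 rises from 1.7% to 14.7%.
- 20% and 40%, the opposite imbalance: 3.36, so the bias runs the other way.

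**The case against.** The strongest reply is that the criterion concerns the woman, not the foetus. Its wording refers to women, footnote 9 speaks of malformations in the mother, the note under Table 7 lists it under the mother, and Section 9.9 describes the paternal equivalent as parental history. Table 5 admits to the MCM cohort all pregnancies ending in spontaneous abortion, termination or stillbirth, and Section 9.3.2 counts a termination for MCM as a case. Reading the criterion as maternal satisfies all of this. The current-pregnancy clause stands only in Figure 3 and says where history may be found; it does not redefine history. Section 9.3.2 also reads MCM at the end of pregnancy or from birth, so the same code is not shown to serve both purposes. Code lists are to be finalised in the SAP.

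Most of this stands as evidence of intent. A reader might infer that the protocol instructs analysts to drop foetal malformation cases; no passage says so. Intent does not repair the window, though. The time limit is fixed in the protocol, and STEP 3 feeds every cohort, so the records used for it under Figure 3 bear on the MCM cohort as well.

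A fair point also concerns the remedy. A mother's congenital condition is lifelong and the minimum look-back is only 12 months, so a cut at LMP2 may keep some women the criterion is meant to exclude.

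**Conclusion.** The point holds as an unguarded overlap. The exclusion window covers the period in which foetal malformations are diagnosed, the protocol allows current-pregnancy records for this criterion, and nothing separates maternal from foetal codes. A foetal malformation coded before the end of pregnancy can therefore exclude an MCM case from the first primary analysis.

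The size cannot be derived from the document. The share of cases coded before the end of pregnancy, and any difference between groups, are assumed throughout. The results above are scenarios at 10% uptake and 7% risk.

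Two stronger conclusions are tempting but unsupported. One is that the bias must favour ruling out 2.5. That needs more loss among exposed than comparator cases, and the protocol gives no reason to expect it: both groups have moderate to severe SLE, equal loss leaves a true RR of 1 unchanged, and the opposite imbalance raises the RR. The other is that nearly all non-live cases would be lost; no figure in the document supports that.

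**What to change.** - In STEP 3 of Section 9.2.2, the note under Table 7 and note d of Figures 1–4, restate the criterion as the mother's own malformation, chromosomal abnormality or genetic syndrome recorded before LMP2.
- Delete the current-pregnancy clause in note d of Figure 3, or restrict it to the mother's own condition.
- Add one sentence: malformation codes first appearing in the mother's record between LMP2 and the end of pregnancy are outcome information for the index pregnancy and never an exclusion.
- Supply the separate list that footnote 9 promises when the code lists are finalised.

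This changes wording only; no data or timelines are affected. The cost is that some women whose own condition is first coded during pregnancy stay in the cohort. Their number cannot be derived from the protocol.
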